8.3.5 SERIOUS ADVERSE EVENT REPORTING

The study clinician will report to the IRB any serious adverse event related or potentially related to the study intervention. All serious adverse events (SAEs) will be followed until satisfactory resolution or until the site investigator deems the event to be chronic or the participant is stable.

POTENTIAL SERIOUS ADVERSE EVENT mentioned in section 8.3.2

Monitoring: Participants will be on continuous telemetry recording continuously the EKG, respiratory rate, oxygen saturation, Blood pressure will be recorded one-hour post-stimulation and 1-4 hours afterwards. Vital signs will be recorded before and directly after stimulation, the medical professional will be at bedside during the stimulation monitoring any side effect. Vital signs and neurologic examination are evaluated every 1-4 hours and as needed afterwards. The VNS will be performed in the intensive care unit setting, where personnel are trained in cardiopulmonary resuscitation and treating hemodynamically unstable patients.

Actions:

- Participants must have stable vital signs (SBP> 100mmHg, MAP>60 mmHg, HR> 60 beats/minute, oxygen saturation > 90%, not on mechanical ventilation) before the vagus nerve is stimulated. If unstable vital signs, the stimulation will be skipped, until the patient is more stable.
- If the participants develop a life-threatening arrhythmia thought to be due to the VNS, subject will be taken off therapy, but will continue to be followed until end of study.
- If the participants get intubated or develops hemodynamic shock due to the natural history of the disease, the subject will be taken off the therapy.

The study investigator shall complete an Unanticipated Adverse Device Effect Form and submit to the reviewing Institutional Review Board (IRB) as soon as possible, but in no event later than 7 working days after the investigator first learns of the effect. The principle investigator is responsible for conducting and evaluating any unanticipated adverse device effect and shall report the results of such evaluation to the reviewing IRB and participating investigators within 7 working days of the event.

8.3.6 REPORTING EVENTS TO PARTICIPANTS

Participants will be directly informed of side effects considered to be related to the VNS.

8.3.7 EVENTS OF SPECIAL INTEREST

Not applicable.

8.3.8 REPORTING OF PREGNANCY

Not applicable, only woman with negative pregnancy test will be enrolled in this inpatient trial

8.4 UNANTICIPATED PROBLEMS

8.4.1 DEFINITION OF UNANTICIPATED PROBLEMS (UP)

The Office for Human Research Protections (OHRP) considers unanticipated problems involving risks to participants or others to include, in general, any incident, experience, or outcome that meets **all** of the following criteria:

 Unexpected in terms of nature, severity, or frequency given (a) the research procedures that are described in the protocol-related documents, such as the Institutional Review Board (IRB)-approved research protocol and informed consent document; and (b) the characteristics of the participant population being studied;

- Related or possibly related to participation in the research ("possibly related" means there is a reasonable possibility that the incident, experience, or outcome may have been caused by the procedures involved in the research); and
- Suggests that the research places participants or others at a greater risk of harm (including physical, psychological, economic, or social harm) than was previously known or recognized.

8.4.2 UNANTICIPATED PROBLEM REPORTING

The investigator will report unanticipated problems (UPs) to the reviewing Institutional Review Board (IRB). The UP report will include the following information:

- Protocol identifying information: protocol title and number, PI's name, and the IRB project number;
- A detailed description of the event, incident, experience, or outcome;
- An explanation of the basis for determining that the event, incident, experience, or outcome represents an UP;
- A description of any changes to the protocol or other corrective actions that have been taken or are proposed in response to the UP.

To satisfy the requirement for prompt reporting, UPs will be reported using the following timeline:

- UPs that are serious adverse events (SAEs) will be reported to the IRB within 2 days of the investigator becoming aware of the event.
- Any other UP will be reported to the IRB within 7 days of the investigator becoming aware of the problem.

8.4.3 REPORTING UNANTICIPATED PROBLEMS TO PARTICIPANTS

The participant will be individually informed of any UP. Given that the patients are in the intensive care unit and that most side effects occur during stimulation, the individual will be informed directly (within 3 days) of the unanticipated problems. 3 days in order to make sure that the UP is due to the VNS.

9 STATISTICAL CONSIDERATIONS

9.1 STATISTICAL HYPOTHESES

There are no statistical hypotheses in this study. This is a feasibility pilot study that will allow us to better calculate the sample size for a large randomized control study comparing VNS to sham device.

The primary outcome measurements for effectiveness will be:

-The difference between the active and sham treatment groups in mean daily morphine equivalence dosage during the study period

Secondary endpoints include descriptive comparisons between the active and sham treatment groups in:

- The difference between the active and sham treatment groups in mean daily headache intensity during the study period

- The difference between total overall morphine equivalence dosage between the active and sham group per subject during study

-Opiate related adverse events (such as urinary retention, constipation, sedation, nausea, vomiting and pruritis)

Exploratory analyses will include comparisons of the rates of stroke, vasospasm, DCI, seizure, central fever and severity of vasospasm between the active and sham treatment groups.

9.2 SAMPLE SIZE DETERMINATION

There are no statistical hypotheses in this study, and therefore there is no sample size justification for this study. This is a feasibility pilot study that will allow us to better calculate the sample size for a large randomized control study comparing VNS to sham device.

9.3 POPULATIONS FOR ANALYSES

Participants who received at least 1 stimulation will be included in the Intent To Treat (ITT) population. Opiate usage and pain intensity during the days of procedures in which patients are intubated and unconscious will be excluded from the analysis. The days of EDV weaning will be noted, given that hydrocephalus can cause headache due to high ICP. A modified Intent-to-treat (mITT) population inclusive of all subjects who treat at least 7 days with at least 3 stimulations of the study device; and a per-protocol (PP) population of people who are compliant with the treatment regimen for the duration of the study will be analyzed.

9.4 STATISTICAL ANALYSES

9.4.1 General Approach

Discrete variables will be tabulated by frequency and proportion of subjects falling in each category.

Continuous variables will be summarized using mean, standard deviation, median, minimum and maximum values.

9.4.2 ANALYSIS OF THE PRIMARY EFFICACY ENDPOINT(S)

-The difference between the active and sham treatment groups in daily mean morphine equivalence dosage during the study

Repeated measures mixed models will be used to describe the difference between the active and sham treatment groups in morphine equivalence dosage during NSCU length of stay. Morphine equivalence dosage will be modeled as a function of treatment group and measurement time. Subject will be included as a random effect. Least squared means will be used to estimate the treatment effect.

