Study Population:	This is a pilot study of 40 subjects. We will enroll men and woman 18 – 75 years of age. Patients with alcohol and drug addiction will be

	excluded. Our patient population mostly represents the New York state area, mostly Long island and Queens as we are the main referral hospital to that area.
Phase:	N/A
Description of Sites/Facilities Enrolling Participants:	The Northwell system has a policy that most subarachnoid hemorrhages admitted to our affiliated hospitals get transferred to the Northshore University Hospital Neurosurgical Care Unit as it is the tertiary Neuro-interventional and Neurosurgical Unit of the system. As a result, those patients are automatically transferred to our unit, where screening and enrollment can be initiated.
Description of Study Intervention:	The intervention consists of a transcutaneous non-invasive stimulation of the cervical branch of the vagus nerve (nVNS) using gammaCore, an FDA approved device for the treatment of migraine and cluster headache. This will be compared to the sham device, which is the same device which does not stimulate the nerve. Stimulation frequency will be identical to the frequency used in previous nVNS studies for the treatment of migraine headache. Dosing will be as described in this protocol. The IRB approved healthcare provider will show the subject how to stimulate the cervical branch of the Vagus nerve transcutaneously, and will increase the amplitude/intensity gradually. If pain or discomfort is felt, the amplitude will be decreased to a comfortable level. Rescue pain killers (acetaminophen, opiates) will be given as needed. In the sham group, the sham device will be applied in the same location and at the same frequency as in the treatment group.
Study Duration:	Study period is up to 10 days starting 24 hours post successful treatment of the aneurysm.

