3 OBJECTIVES AND ENDPOINTS

The primary outcome measurement for effectiveness is:

-The difference between the active and sham treatment groups in mean daily morphine equivalence dosage during study

Secondary endpoints include descriptive comparisons between the active and sham treatment groups in:

- The difference in mean daily headache intensity during the study

The difference between total overall morphine equivalence dosages per subject during study
 Opiate related adverse events (such as urinary retention, constipation, sedation, nausea, vomiting and pruritis)

- The difference in cytokines levels and brain permeability markers in the blood and/or CSF before and after stimulation and between the sham and active device group

- Effects of VNS on brain permeability measured through CT perfusion studies

-The difference in modified rankin scale at hospital discharge and during outpatient follow up. This will be collected retrospectively from the follow up outpatient visit.

Exploratory analyses will include descriptive comparisons of the rates of stroke, vasospasm, DCI, seizure, central fever and severity of vasospasm between the active and sham treatment groups.

OBJECTIVES	ENDPOINTS
Primary Objective:	

Incidence of device related serious adverse events.	Proportion of patients with device related adverse events
The difference between the active and sham treatment groups in mean daily morphine equivalence dosage during study	Morphine equivalence dosage will be calculated per day.
Secondary Objectives	
The difference between the active and sham treatment groups in the mean daily headache intensity during the study	Headache intensity will be measured throughout the day and a mean daily headache intensity will be calculated.
The difference between total overall morphine equivalence dosage between the active and sham group per subject during study	Total morphine equivalence dosage for the duration of the study will be calculated.
Incidence of opiate related adverse events (such as urinary retention, constipation, sedation, respiratory depression, nausea, vomiting and pruritis)	Number of patients with of urinary retention, constipation, sedation, nausea, respiratory depression, vomiting and pruritis.

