5.5 STRATEGIES FOR RECRUITMENT AND RETENTION

The neurosurgical critical care unit (NSCU) at Northshore University Hospital is the main referral unit for the healthcare system for patients with subarachnoid hemorrhage. All transferred patients

are admitted to the NSCU, as a result, patients can be easily identified by the research team on a daily basis. Every day, the neurointensivist or the research coordinator will evaluate which patients admitted to the NSCU have been diagnosed with subarachnoid hemorrhage. If an aneurysm is found to be the cause of the SAH, surgical or endovascular treatment of the aneurysm is typically performed within 72 hours of diagnosis. Patients will be included in the study once the aneurysm has been treated. The primary investigator, or sub investigators will take consent from the patient. The primary investigator will ensure that the sub investigators and research assistants are trained and knowledgeable of the research protocol. Patients enrolled in the study will be followed up to 10 days starting 24 hours post successful treatment of the aneurysm unless discharged earlier from the hospital.

We admit on average 110 SAH cases a year. If we assume that 50% satisfy our inclusion criteria, and that 70% will sign the inform consent, we should be able to reach our target number in approximately 12 months. Patients identified in the NSCU will be approached by the research team, and the study will be explained to them.

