8 STUDY ASSESSMENTS AND PROCEDURES

8.1 EFFICACY ASSESSMENTS

Per standard of care, patients presenting with signs of SAH like acute severe headache, will get a diagnostic head CT which confirms blood in the subarachnoid space. If patients have symptomatic hydrocephalus (altered mental status with CT head consistent with hydrocephalus) an external ventricular drain will be placed. Most patients will get either a CT angiogram or a conventional angiogram to rule out a vascular malformation, especially if there is no history of trauma. If an aneurysm is detected, the standard of care is to treat it as soon as possible. Usually, an aneurysm iseither coiled or clipped (craniectomy or craniotomy). Every patient admitted with subarachnoid hemorrhage will get graded accordingly to their headache intensity, level of consciousness and neurologic deficits with the Hunt Hess grade (table 2). Their CT scans also get graded (modified fisher scale mFS) according to the thickness and location of blood (table 3). All subarachnoid hemorrhage (unless there is minimal amount of blood and no vascular malformation) are admitted to the Neurosurgical care unit (NSCU). Detailed physical examination, including the NIHSS, history, including medication history, past medical, surgical history, and social history are recorded in the medical records. North Shore University hospital NSCU is the referral center for most of the hospitals in Northwell health care system. Most aneurysmal SAH patients get transferred to our unit. Per standard of care, all women of child bearing age, admitted to the NSCU get a urine or blood pregnancy test, patients suspected of abusing drugs get urine toxicology. Once in the NSCU, patients get vital signs and neurologic assessment every hour, and pain assessment every 4 hours and as needed. The length of stay in the intensive care unit depends on the amount of blood on the head scan (mFS). Patients with higher mFS are more prone to get delayed cerebral ischemia. As a result, per standard of care, patients with SAH get almost daily transcranial dopplers to monitor for cerebral vasospasm, frequent head scans, occasionally brain perfusion studies and MRI of the brain. Patients are monitored for central fever (vital signs, blood cultures), cerebral salt wasting with frequent BMP and urine output measurements, seizures with PRN electroencephalograms (EEG). Once out of the critical care period, (vasospasm usually starts at day 3 post bleeding and peaks at day 10), patients get transferred to a regular neurosurgical floor before being discharged home or to rehabilitation. On average patients stay in the NSCU between 2-21 days. All patients admitted to the NSCU with SAH will be screened and evaluated for the inclusion and exclusion criteria after obtaining an informed consent.

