- Constipation evaluated by the need for enema, suppository, lactulose or magnesium oxide administered
- Blood tests, CSF studies
- EEG results
- Neurologic examination including Glasgow coma score, and NIHSS
- Delirium score

When Transcranial dopplers are being done as per standard of care, we will assess the changes in transcranial velocities around the time of the stimulation of the Vagus nerve.

When possible, we will draw blood or in case there is an EVD we will also collect CSF for biomarkers. Not more than 5 ml of blood will be drawn before the 11:30 am stimulation session of the Vagus nerve. This will be repeated approximately 24 hours later, at 11:30 am post VNS stimulation session. This might be repeated on days 5 and 7 post-ictus In case there is an EVD, 2 cc of CSF from the drain and 20 cc of CSF that is otherwise discarded will be drawn before the 11:30 am stimulation session of the Vagus nerve. Another 2 cc of CSF from the drain and 20 cc of CSF that is otherwise discarded will be drawn before the 11:30 am stimulation session of the Vagus nerve. Another 2 cc of CSF from the drain and 20 cc of CSF that is otherwise discarded will be drawn approximately 24 hours later, at around 11:30 am post VNS stimulation session. This might be repeated on days 5 and 7 post-ictus.

The CSF will not be taken from the proximal port of the EDV unless it is being tested for CSF cell count or cultures as per standard of care. This is in order not to increase the risk of infection.

Deidentified blood and CSF will be sent to [name], academic chief in the department of stroke and vascular neurology, Yale, [name].

IF CT perfusion is being performed per standard of care between days 3-10, blood brain permeability will be evaluated and results will be compared between the sham group and the active device group.

During the period of the study after the patients are discharged from the ICU to the Neurosurgical floor, we will evaluate their daily headache intensity and morphine equivalence dosage, in addition to their TCD results, Neuroimaging and EEG results, neurologic examination and vital signs.

Table 2: Hunt-Hess Score in aneurysmal SAH: (26, 27)

- 1. Asymptomatic, mild headache, slight nuchal rigidity
- 2. Moderate to severe headache, nuchal rigidity, no neurologic deficit other than cranial nerve palsy
- 3. Drowsiness, confusion, mild focal neurologic deficit
- 4. Stupor, moderate-severe hemiparesis
- 5. Coma, decerebrate posturing

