9.4.3 ANALYSIS OF THE SECONDARY ENDPOINT(S)

- The difference between the active and sham treatment groups in mean headache intensity during study period

Repeated measures mixed models will be used to describe the difference between the active and sham treatment groups in mean headache intensity during NSCU length of stay. Pain will be modeled as a function of treatment group and measurement time. Subject will be included as a random effect. Least squared means will be used to estimate the treatment effect.

- The difference between total overall morphine equivalence dosage between the active and sham group per subject during study

Total overall morphine equivalence dosage in the active and sham treatment groups will be compared using analysis of covariance (ANCOVA) with adjustment for number of days in study.

-Opiate related adverse events (such as urinary retention, constipation, sedation, nausea, vomiting and pruritis)

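### The primary opioid model and the headache model are limited to the NSCU stay, but the endpoints are defined over a study period of up to 10 days that ends early only at hospital discharge

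*Protocol*

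**What the plan says.** **Endpoint.** Protocol section 3 gives the primary effectiveness outcome as "The difference between the active and sham treatment groups in mean daily morphine equivalence dosage during study". Section 9.1 repeats it: "groups in mean daily morphine equivalence dosage during the study period". The heading line of section 9.4.2 also refers to the whole study.

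**Length of the study.** The synopsis (1.1) states: "Study period is up to 10 days starting 24 hours post successful treatment of the aneurysm". Section 5.5 says enrolled patients are "followed up to 10 days starting 24 hours post successful treatment of the aneurysm unless discharged earlier from the hospital". Leaving the NSCU does not end the study period.

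**Model.** Directly under its heading line, 9.4.2 uses a repeated measures mixed model for the difference between the "active and sham treatment groups in morphine equivalence dosage during NSCU length of stay". Section 9.4.3 has the same restriction for the "sham treatment groups in mean headache intensity during NSCU length of stay". The total-dose ANCOVA in 9.4.3, however, adjusts for days in study, so that section uses two windows.

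**Floor data.** Section 8.1 says that, during the study and after transfer from the ICU to the floor, "we will evaluate their daily headache intensity and morphine equivalence dosage". The schedule of activities (1.2) marks daily narcotic use in the step-down/floor column.

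**NSCU stay.** Section 8.1: "On average patients stay in the NSCU between 2-21 days". No distribution is given.

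**SAP.** The Efficacy Analysis section fits an MMRM with treatment contrasts from Day 1 to Day 14 and makes the Day 14 contrast the primary comparison.

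**The concern.** The quantity that 9.4.2 estimates is not the endpoint that section 3 defines. Two things are at stake.

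First, floor data that belong to the endpoint, and that the protocol arranges to collect, are left out of the model. A mixed model could make up for absent days only under an assumption about how floor use relates to NSCU use. There is no reason to rely on that when the values are on file.

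Second, the number of days each patient contributes is set by ICU discharge, which comes after randomisation. Section 8.1 ties NSCU stay to the amount of blood on the scan, so the later modelled days come increasingly from patients with more blood. Section 2.3.2 names a shorter ICU stay as a possible benefit of nVNS. If that happened, the arms would be compared over different days.

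The trial's stated purpose is to inform the sample size of a larger trial (9.2). The difference and variance carried forward depend on which days are analysed.

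**Working it through.** There is no sample size, power or effect figure behind this point to reproduce. The check is a comparison of windows and a count of days.

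**1. The windows side by side**

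| Source | Window |
|---|---|
| Protocol 3, 9.1, heading line of 9.4.2 | The study |
| Protocol 1.1, 5.5 | Up to 10 days, or hospital discharge if earlier |
| Protocol 9.4.2 and 9.4.3, model sentences | NSCU stay |
| SAP, Efficacy Analysis | Days 1 to 14, primary contrast at Day 14 |

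**2. Day counts for single patients**

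Inputs: a study period of 10 days (1.1, 5.5) and an NSCU stay L within the stated 2-21 days (8.1). Assumption: study day 1 falls on NSCU day s. The documents do not give s, so I vary it from 1 to 6.

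- Study days inside the NSCU = max(0, min(L, s+9) − s + 1)
- Study days lost = 10 − that count. This is an upper limit, reached if the patient is still in hospital on study day 10.
- On a literal reading of NSCU stay only: NSCU days after the study period = max(0, L − (s+9)), and NSCU days before it = min(L, s−1)

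| s | L | Study days in NSCU | Lost (up to) | NSCU days after (literal) | NSCU days before (literal) |
|---|---|---|---|---|---|
| 1 | 2 | 2 | 8 | 0 | 0 |
| 1 | 7 | 7 | 3 | 0 | 0 |
| 1 | 14 | 10 | 0 | 4 | 0 |
| 1 | 21 | 10 | 0 | 11 | 0 |
| 2 | 2 | 1 | 9 | 0 | 1 |
| 2 | 7 | 6 | 4 | 0 | 1 |
| 2 | 21 | 10 | 0 | 10 | 1 |
| 6 | 7 | 2 | 8 | 0 | 5 |
| 6 | 14 | 9 | 1 | 0 | 5 |
| 6 | 21 | 10 | 0 | 6 | 5 |

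Example for s = 2, L = 7: min(7, 11) − 2 + 1 = 6 days kept, so up to 10 − 6 = 4 lost.

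The loss of study days does not depend on how the NSCU phrase is read. It arises whenever L < s + 9 and the patient remains in hospital. The added days arise only on the literal reading. These rows show a possible range for single patients, not a trial average.

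**3. After the correction**

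With the defined study period as the window, no study day is lost to ICU discharge and no NSCU day after study day 10 is added. No stated power or sample size changes, because none is stated.

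**The case against.** **The NSCU phrase may mean NSCU days within the study.** It stands under a heading line that refers to the study, so this reading is fair. A reader might infer that the model certainly adds ICU days after the device period; the text does not force that. On the narrower reading the added days vanish, but the lost floor days and the dependence on ICU discharge remain.

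**The NSCU window may be intended.** The synopsis and the SAP overview frame the hypothesis on the ICU stay. That hypothesis concerns headache intensity and frequency, not opioid dose, and it does not make 9.4.2 agree with section 3.

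**Floor days may be off-device.** A reader might infer that the omitted days are treated days. The schedule in 1.2 marks the intervention on the floor, but the flow chart in 8.2 runs it until ICU discharge and 8.3.5 places it in the ICU setting. The documents do not settle this. The endpoint definition and the floor data collection stand either way.

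**The size could be modelled.** Suppose NSCU stay were uniform over 2-21 days. If study day 1 followed 0, 1 or 3 NSCU days, 66/230 = 29%, 55/210 = 26% or 36/171 = 21% of modelled days would fall after the device period on the literal reading. After 5 or 8 days this drops to 21/136 = 15% or 6/91 = 7%. The uniform shape and the offset are both invented. A diluted effect in mg/day would also need an assumed effect, no carry-over and a weight per patient-day that a random-subject model does not use. None of these is supported as an estimate.

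**Hospital discharge is post-randomisation too.** This stands. Section 2.3.2 names ICU and hospital stay together. The corrected window still ends at hospital discharge, but that is the protocol's own definition and it no longer discards collected days.

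**This is a pilot, and 9.4.2 only describes a difference.** That lowers the consequence. The SAP nevertheless tests at a two-sided 0.05 level.

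**Conclusion.** The point holds. The model sentences in 9.4.2 and 9.4.3 use a window that differs from the one in sections 3 and 9.1. As written, they leave out collected study days for any patient who moves to the floor before the study period ends, and they make the analysed days depend on ICU discharge. Section 2.3.2 says only that nVNS might shorten the ICU stay, so a bias between arms is possible but not predicted by the protocol.

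The size is open. A single patient may lose no days or nearly all 10, depending on NSCU stay and the assumed s. Neither the average loss nor the effect on the estimate can be computed from a bare 2-21 day range. Added post-device days are a further possibility on the literal reading only.

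The SAP does not resolve the matter. It is dated May 2022, before protocol version 6 of January 2023, and its Day 14 contrast lies outside a 10-day study period. The plan should be corrected before analysis so that the window is not chosen after results are seen.

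**What to change.** - In 9.4.2 and 9.4.3, replace the NSCU restriction with the defined study period: up to 10 days, whether in the NSCU, step-down or floor, ending at hospital discharge if earlier.
- State one day-1 origin. The synopsis and 5.5 count from aneurysm treatment, 8.1 starts treatment at NSCU admission, and the flow chart in 8.2 ends at day 10 after ictus. The origin must also work for eligible patients who have no aneurysm to treat.
- Align the SAP's Day 1-14 model and its Day 14 primary contrast with that window.
- Keep the NSCU-only analysis as supportive, with its days defined.
- Reconcile sections 1.2, 8.2 and 8.3.5 on whether stimulation continues on the floor, so that the treatment status of floor days is clear when results are read.

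Cost: wording in two protocol sections, and a revised visit range and primary contrast in the SAP, which is more than an edit of words. No new data are needed, because floor opioid dose and headache intensity are already to be collected.

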1.2 SCHEDULE OF ACTIVITIES (SOA)

Procedures	Screening and randomization Days -1-5	Enrollment/Baseline Days 2-5 till discharge from NSCU	Step down unit Neurosurgical floor	Final Study discharge
Informed consent	Х			
Demographics	х			
Medical history	Х			
Administer study intervention		Х	x	
Concomitant medication review	х	Х	х	x
Physical exam (including height and weight)	х	Х	x	х
Vital signs (temperature, BP, HR, Oxygen saturation)	х	Hourly and as needed	x	х
Height	Х			
Weight	Х	Х		Х
Performance status	Х	Х	x	Х
Hematology	Х	Х	x	
serum chemistry	Х	Х	X	
Pregnancy test	Х			
EKG (as indicated)	Х	х	As needed	
Daily narcotic use	х	х	x	
Adverse event review and evaluation	х	х	x	x
Radiologic/Imaging assessment (CT, MRI, CTA/CTP, angiogram)	х	х	x	x
Patient satisfaction assessment				x
Complete Case Report Forms (CRFs)	х	х	x	Х

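### The protocol's mixed models for morphine dose and headache intensity cover only the NSCU stay, while both endpoints cover a study period of up to 10 days that includes floor days

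*Protocol*

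**What the plan says.** Protocol section 3 gives the primary effectiveness outcome as the difference in "mean daily morphine equivalence dosage during study", and section 9.1 as the difference in "mean daily morphine equivalence dosage during the study period". Section 9.1 defines mean daily headache intensity over the same period. The synopsis fixes the length: "Study period is up to 10 days starting 24 hours post successful treatment of the aneurysm". Section 5.5 lets hospital discharge end this follow-up early; it does not mention NSCU discharge.

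The models are narrower. The lead line of 9.4.2 repeats the study-wide endpoint, but the sentence that specifies the mixed model estimates the difference "in morphine equivalence dosage during NSCU length of stay". In 9.4.3 the headache model does the same: "in mean headache intensity during NSCU length of stay". The total-dose analysis in 9.4.3 has no such limit; it is an "analysis of covariance (ANCOVA) with adjustment for number of days in study".

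Floor data are planned. For the time after transfer from the ICU, section 8.1 says "we will evaluate their daily headache intensity and morphine equivalence dosage". The schedule in 1.2 marks "Daily narcotic use" and the study intervention in the step-down and floor column as well as in the NSCU column.

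The SAP states its primary objective over the study and sets no NSCU limit. Its model runs by visit from Day 1 to Day 14, with the primary comparison at Day 14. It also plans an overall contrast. The hypothesis in the synopsis and in the SAP overview refers to the ICU stay.

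**The concern.** Followed as written, 9.4.2 estimates something other than the stated primary endpoint. Its model contains treatment group and measurement time, with no interaction between them. The treatment effect is therefore an average over whichever days enter, and changing the days changes the quantity whenever the effect varies over time.

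The end of the window is also a post-randomisation event. Section 2.3.2 suggests that nVNS could shorten the ICU stay by lowering opiate use. If it does, the two arms would contribute different sets of days, for a reason tied to the primary outcome.

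Sections 9.1 and 9.2 justify the pilot by its use in sizing a larger trial. An effect estimate carried forward for that purpose needs one stated window. At present there are three candidates (NSCU stay, 10-day period, Day 14), and neither document says which prevails.

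**Working it through.** The plan gives no figure to reproduce. The check sets the windows side by side and then counts days.

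**Windows**

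- Endpoint: study period, up to 10 days, ended early by hospital discharge (Protocol 1.1, 3, 5.5, 9.1).
- Collection: NSCU, step-down unit and floor (Protocol 1.2, 8.1), continuing to hospital discharge (4.4).
- Models in 9.4.2 and 9.4.3 (headache): NSCU stay.
- SAP primary contrast: Day 14. If Day 1 is the first study day, this is 14 − 10 = 4 days after the period ends.

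**Inputs for the day count**

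- Study period of 10 days (Protocol 1.1).
- NSCU stay L of 2 to 21 days (Protocol 8.1). No distribution is given.
- Assumptions: NSCU days are counted from study day 1, and the patient is in hospital through day 10.

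**Formulas**

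- Study days in the model = min(10, L)
- Study days left out = 10 − min(10, L)
- Days after day 10 let in by a literal reading = max(0, L − 10)

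| L (NSCU days) | Study days in model | Study days left out | Days after day 10 let in |
|---|---|---|---|
| 2 | 2 | 8 | 0 |
| 5 | 5 | 5 | 0 |
| 7 | 7 | 3 | 0 |
| 10 | 10 | 0 | 0 |
| 14 | 10 | 0 | 4 |
| 21 | 10 | 0 | 11 |

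**Sensitivity to the first assumption.** Suppose s NSCU days have passed before study day 1, and replace L by max(0, L − s). For s = 2 to 4, a 7-day stay leaves out 10 − 5 = 5 to 10 − 3 = 7 study days, and a 2-day stay leaves out all 10. A 21-day stay lets in 19 − 10 = 9 down to 17 − 10 = 7 days after day 10.

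**Effect on the estimate.** If the daily effect is the same on every day, the NSCU average and the study-period average are equal. If the effect builds over time, dropping late days lowers the average; if it fades, dropping them raises it. The documents give no effect shape, so neither sign nor size follows.

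**The case against.** The NSCU wording may be deliberate. The hypothesis is framed on the ICU stay, and Protocol 8.3.5 places stimulation in the intensive care unit. That is a possible reading. But sections 3 and 9.1 do not define the endpoints that way, and the schedule continues the intervention on the floor.

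The SAP partly repairs the problem: it has no NSCU limit and already plans an overall contrast. This stands, and it makes the remedy easy. It does not settle the matter. The SAP's primary comparison is at Day 14, and the SAP is dated May 2022, whereas the protocol that still carries the NSCU wording is Version 6 of January 2023.

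Informative exit is not peculiar to the NSCU. Section 2.3.2 names hospital stay as well, so a window ending at hospital discharge also relies on a missing-at-random assumption. This stands as a limit of the fix. That assumption would also cover NSCU exit driven by recorded doses, but it would not say which window is the endpoint.

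This is a 40-patient feasibility pilot without formal hypotheses in the protocol, and 9.4.2 is descriptive. That lowers the stakes, although the SAP does test at the 0.05 level.

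Two stronger readings are tempting.

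- A reader might infer that at most 3 of 10 days are lost, because the SAP's primary set requires at least 7 treated days. That joins the SAP's set to the protocol's model. The SAP model has no NSCU limit, Protocol 9.3 does not name that set as primary, and floor days could count towards the 7.
- A reader might infer a definite bias. Suppose every patient left the NSCU after day 7. Over Days 2 to 10, an effect proportional to (t − 1) would give 3.5/5.0 = 70% of the period average, and one proportional to (10 − t) would give 5.5/4.0 = 138%. These are constructed cases. The documents support neither a common exit day nor either shape.

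**Conclusion.** The conflict holds and should be corrected. As written, the primary model and the headache-intensity model cover a different window from their endpoints. Per patient they omit 0 to 8 of 10 study days, on the assumptions that NSCU days count from study day 1 and that the patient is in hospital through day 10. They also admit up to 11 days after day 10 for a 21-day stay. How many patients fall where is unknown.

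The resulting error in the treatment effect cannot be sized or signed from the documents. It is nil if the daily effect is constant, and the practical impact is small if most patients stay in the NSCU for the whole period. The total-dose ANCOVA is not affected. The finding is that the primary quantity is not uniquely defined; it is not that the trial's estimate is shown to be biased.

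**What to change.** In Protocol 9.4.2 and the 9.4.3 headache model, replace the NSCU limit with: *during the study period (post-randomisation days up to day 10 or hospital discharge, including step-down and floor days)*.

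State that the window starts at the first study stimulation for every patient. This is needed because enrolment may be up to 5 days after aneurysm treatment while the synopsis starts the clock at 24 hours, and because eligible patients without a treated aneurysm have no such clock. State what day 10 is counted from, and bring the synopsis into line.

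In the SAP, limit visits to the same period. Make the already planned overall contrast, taken over post-baseline days, the primary comparison in place of Day 14. With the SAP's Day 1 baseline used as a covariate, and Day 1 as the first study day, these are Days 2 to 10.

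Align the ICU-stay wording of the hypothesis in both documents. Keep an NSCU-only analysis as a labelled sensitivity analysis.

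The cost is a protocol and SAP amendment with IRB review. It is more than an edit of wording, because the SAP's primary contrast changes. Days after hospital discharge would be treated as missing at random, which should be stated. No new data, visits or staff are needed.
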